6. STUDY PROCEDURES

6.1 Schedule of Evaluations

	Screening	Evaluation Period								Treatment 1 Month 3			WASHOUT Month 4	Treatment 2 Month 5			Follow-Up: Final Visit				
		Month 1				Month 2				Menstrual Cycle Day 10	Ovulation* (Luteinizing Hormone surge – LHS)	LHS → LHS+2 days*		LHS → LHS+10 days	LHS+8 → LHS+9 days	Menstrual Cycle Day 10		Ovulation* (Luteinizing Hormone surge – LHS)	LHS → LHS+2 days*	LHS → LHS+10 days	LHS+8 → LHS+9 days
		Eval WK1	Eval WK2	Eval WK3	Eval WK4	Eval WK5	Eval WK6	Eval WK7	Eval WK8												
Screening Consent	X																				
Urine Toxicology Screen	X														X						
Menstrual Assessment Questionnaire	X																				
Ovulation Testing (7 days)									X												
Hamilton		X	X	X	X	X	X	X	X						X					X	X
BDI		X	X	X	X	X	X	X	X						X					X	X
BAI		X	X	X	X	X	X	X	X						X					X	X
PGWI		X	X	X	X	X	X	X	X						X					X	X
Daily Mood Ratings		X	X	X	X	X	X	X	X						X					X	X
SCID									X												
Study Consent										X											
Randomization										X											
SPAQ										X											
Expectation Form										X											
Horne and Ostberg										X											
PSQI					X				X												X
Visual Analogue Scale Sleep Quality Rating				X				X													X
Actigraphy (10 days)									X					X					X		
Urine Collection (30 hrs)																					X
Side-Effects Checklist																					X
Global Assessment of Treatment Effectiveness																					X

* Evaluations (Hamilton and Becks) over the phone.

6.2 Description of Evaluations

Screening	Evaluation Period								Treatment 1 Month 3			WASHOUT Month 4	Treatment 2 Month 5			Follow-Up: Final Visit				
	Month 1				Month 2				Menstrual Cycle Day 10	Ovulation* (Luteinizing Hormone surge – LHS)	LHS → LHS+2 days*		LHS → LHS+10 days	LHS+8 → LHS+9 days	Menstrual Cycle Day 10		Ovulation* (Luteinizing Hormone surge – LHS)	LHS → LHS+2 days*	LHS → LHS+10 days	LHS+8 → LHS+9 days
	Eval WK1	Eval WK2	Eval WK3	Eval WK4	Eval WK5	Eval WK6	Eval WK7	Eval WK8												
	Menstrual Cycle Day 10																			
									LHS →											
									LHS+10 days											
									LHS+8 →											
									LHS+9 days											

Evaluations will be performed at various times during the multiple steps of this 5-month study: Screening, Evaluation Period (months 1 and 2), Treatment 1 (month 3), Washout (month 4), Treatment 2 (month 5) and Follow-up/Final Visit. In the Schedule of Evaluations figure above, LHS refers to luteinizing hormone surge detected via ovulation testing (performed for 7 days starting on menstrual cycle day 10 in months 2, 3 and 5).

Objective ratings (HRSD and SCID) will be administered, collected, scored and reviewed by the Clinical Rater immediately upon completion by the patient.

Subjective ratings (BDI, BAI, PGWI, Daily Mood Ratings (VAS), SPAQ, Expectation Form, Horne and Ostberg Scale, PSQI, Sleep Quality Ratings, Side Effects Checklists, Global Assessment of Treatment Effectiveness) will be collected and scored by the Research Associate for review by the Clinical Rater upon completion by the patient.

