4.1 Inclusion Criteria

PMDD women wishing to participate in this study must meet the following inclusion criteria:

- Age: 18-45 years.
- Women with regular ovulatory menstrual cycles 26-32 days in length (for at least the previous six months).
- A history of a depressive (but not bipolar) mood disorder, but not an ongoing episode (symptom free for the last 12 months).
- Patients must meet DSM-IV criteria for Premenstrual Dysphoric Disorder (that includes irritability).
- Objective ratings: mean of HRSD total scores across evaluation weeks 1-8 \leq 7 for follicular phase (day 5-10 of cycle after menses); mean of total HRSD

scores across evaluation weeks 1-8 ≥ 14 for premenstrual (luteal) phase (6 days prior to onset of menses onward).

- Subjective ratings: mean of Beck Depression Inventory total scores across evaluation weeks 1-8 < 10 follicular phase; ≥ 10 premenstrual (luteal) phase.
- Daily ratings: minimal symptoms (mean less than 50 on 100mm scale) follicular phase; at least a 30% increase in mean affective symptom ratings, premenstrual (luteal) phase.
- By clinical assessment and ratings, the patient has reported a history (for at least the last six months) of recurrent, moderate to severe premenstrual mood symptoms that impair some aspect of social or occupational functioning and that remit within a few days after the onset of menses. This pattern is prospectively documented with subjective daily mood ratings (DMR – visual analogue scale) during at least two consecutive symptomatic cycles. Symptom severity will also be documented with objective and subjective ratings over that time. Patients must demonstrate a consistency of symptoms and a long enough duration of symptoms (7-10 days) to allow for study.
- Subjects willing to endure the rigors of a long-term (up to 6 months) research study.

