4.2 Exclusion Criteria

Participants meeting any of the following exclusion criteria at baseline will be excluded from study:

- Subjects with significant medical illness including hepatic (abnormal liver function tests), neurological, renal, cardiac, pulmonary, hematologic, gastrointestinal, or metabolic disorders.
- Subjects who are lactating, are within 6 months postpartum, or have an irregular sleep- wake cycle, e.g., from having very young children in the home.
- Subjects who are using hormonal contraception (within six months prior to the study).
- Subjects using medication that may affect outcome measures of mood, circadian rhythms or hormone levels (6-sulphatoxy-melatonin, estradiol, progesterone, FSH, LH, prolactin) within one month of initiating the study or anytime during the study. Such medications include OTC medication (excluding Tylenol), antidepressants, anti-anxiety, antihypertensive, beta blockers, and asthma medications. Vaccinations, vitamins/mineral supplements (excluding St. John's Wart, melatonin and valerian) and/or short course antibiotics will not be considered exclusionary.
- Subjects with significant psychiatric disorder (schizophrenia, bipolar disorder, anxiety disorders, eating disorders, personality disorders, sleep disorders). An ongoing major depressive episode within the last year is reason for exclusion, although a previous history of a depressive episode is not (using DSM-IV diagnostic criteria for a major depressive episode).
- Subjects with a recent history (within the past year) of drug or alcohol abuse.

- Subjects with a history of anemia, liver, kidney, cardiopulmonary, metabolic or thyroid disease within one year of participation (per patient-reported medical history).
- Subjects with irregular menstrual cycles (cycle lengths vary greater than 3 days or who fail to ovulate for 2 consecutive months).
- Subjects unlikely to cooperate with the requirements of the study.
- Subjects needing frequent or continuous use of any medication or drugs that may affect outcome measures, including alcohol (>1 drink daily) and nicotine (> 5 cigarettes daily).
- Subjects whose prospective DMR ratings do not show cyclic variation in association with the menstrual cycle (as per inclusion criteria).

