Duration: Intervention phase will require a minimum of 3 months, provided patients have regular menstrual cycles and we can detect an LH surge (ovulation) in months 3 and 5. If a patient fails to ovulate in either month 3 or 5, she will be asked to repeat ovulation testing the following month. Two consecutive months with no ovulation will result in discontinuation of participation.

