Note, only subjects who meet all of the inclusion criteria and none of the exclusion criteria after successful completion of the evaluation phase are eligible for randomization into the treatment phase.

In addition to violations of inclusion and exclusion criteria, we also will document in the patient's chart reasons for randomization failure, any protocol deviations and reasons why subjects were lost to follow-up, voluntarily withdrew and/or were terminated from the study.

Participants will be assigned for study between cycle days 1 and 10 of Month 3 and will begin the wake therapy component of Treatment 1 at time of ovulation, which may occur between cycle days 10 and 17. Treatment 2 will occur in Month 5, approximately two months after randomization. If a patient does not ovulate, treatment will be delayed until the following menstrual cycle, thereby increasing the time between randomization and each treatment condition by approximately 1 month, the maximum allowable period.

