15. SUPPLEMENTS/APPENDICES

I. Procedures Schedule

Consult Schedule of Evaluations (see section 6.1) for specific evaluations, forms and ratings associated with each time point listed below.

1. Screening:
 - a. Telephone screening to ensure potential participants meet eligibility criteria and to schedule initial in-office screening visit,
 - b. Screening Visit:
 - i. Patient signs Screening Consent
 - ii. Perform urine toxicology screening
 - iii. Complete Menstrual Assessment Questionnaire
 - iv. Record most recent start of menses (Cycle Day 1)
2. Evaluation Month 1
 - a. Evaluation week 1
 - i. Provide patient with binder that includes all required study forms, calendars, checklists and equipment/collection instructions needed in Evaluation Months 1 and 2
 - b. Evaluation week 2
 - c. Evaluation week 3
 - d. Evaluation week 4
3. Evaluation Month 2
 - a. Record Cycle Day 1 (patient will call Study Coordinator with date)
 - b. Evaluation week 5 – (Steps i – iv below must occur before Cycle Day 10):
 - i. Provide Clearblue® ovulation (luteinizing hormone surge-LHS) test kit
 - ii. Provide urine collection kit
 - iii. Provide Actiwatch Spectrum
 - iv. Provide instructions and demonstration of proper form completion, sample collection and equipment use
 - c. Evaluation week 6
 - d. Evaluation week 7
 - e. Evaluation week 8
 - f. The following steps are not categorized within the previous 4 evaluation weeks (5-8) as varying menstrual cycle times make it difficult to determine exactly when each of the following events will occur:
 - i. Menstrual Cycle Day 10 – commence testing for LHS (7 days of testing)
 - ii. Ovulation Day (LHS) – commence actigraphy recording (for 10 days)
 - iii. 8-9 Days after LHS (LHS+8 → LHS+9) – commence urine collection (30 hrs)
 - iv. LHS+11 – equipment, samples and forms are returned to lab
4. Treatment 1 (Month 3)

- a. Record Cycle Day 1 (patient will call Study Coordinator with date and to schedule pre-intervention in-office visit)
 - b. Pre-Intervention Visit – to be completed between cycle days 1 and 10:
 - i. Patient signs the Study Consent
 - ii. Patient is randomized to treatment
 - iii. Provide ovulation test kit
 - iv. Provide urine collection kit
 - v. Provide Actiwatch Spectrum
 - c. Menstrual Cycle Day 10 – commence testing for LHS (7 days of testing)
 - d. Ovulation Day (LHS) – commence actigraphy recording (for 10 days)
 - commence Wake Therapy (1 night)

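### LH testing ends on cycle day 16, but the plan accepts ovulation to day 17 and cycles up to 32 days, so ovulating women with longer cycles can be recorded as not ovulating

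*Combined protocol and SAP*

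**What the plan says.** **Test window.** Section 6.2 says the LH surge is "detected via ovulation testing (performed for 7 days starting on menstrual cycle day 10 in months 2, 3 and 5". Sections 6.2.2 and 6.2.4 repeat this, and the procedures schedule in section 15 says, for cycle day 10, "commence testing for LHS (7 days of testing". The start day is the same for every woman.

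**Accepted ovulation days.** Section 6.2.2 starts wake therapy "at time of ovulation, which may occur between cycle days 10 and 17".

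**Eligible cycles.** Section 4.1, repeated in section 9.3, requires "Women with regular ovulatory menstrual cycles 26-32 days in length (for at least the previous six months". Section 4.2 excludes women whose "cycle lengths vary greater than 3 days or who fail to ovulate for 2 consecutive months", so variation of up to 3 days is tolerated.

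**When no surge is found.** Section 3 excludes the woman for that month and postpones the study to a later month in which ovulation is documented. Section 5.1 repeats testing the next month if Month 3 or 5 fails, then: "Two consecutive months with no ovulation will result in discontinuation of participation". Section 10.3.3 postpones further testing when staff do not agree that ovulation has occurred, but adds no test days within the cycle.

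**The concern.** The plan equates a detected surge with ovulation: section 5.1 gives ovulation in brackets as another name for the LH surge, and section 15 labels the surge day as ovulation day. A surge after day 16 therefore looks the same as an anovulatory cycle, and the postponement and discontinuation rules apply to it.

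The wake night, the light days, the treatment-month ratings, actigraphy and urine collection are all timed from the surge. A miss in Month 2 delays the baseline urine and actigraphy. A miss in Month 5 lengthens the gap between the two treatment periods, and a second miss there loses the second period of the crossover. Such losses would fall mainly on women with longer cycles. The target is 40 completers from 48 recruited, and section 4.3 expects about 5% of those screened to qualify, so avoidable losses are expensive.

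**Working it through.** **1. Reproduce the plan's day counts.** With a surge on day 14 (section 3), days 1-7 after it are cycle days 15-21, days 8-9 are 22-23 and day 10 is 24. All match Figure 1.

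**2. Last test day.** 10 + 7 − 1 = 16. Day 17 in section 6.2.2 is not reproduced. It would need 8 tests (10 + 8 − 1 = 17), or ovulation dated one day after a day-16 surge, which conflicts with section 15, where the two are the same day.

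**3. Expected surge day by cycle length.** Expected day = cycle length − surge-to-menses interval. The interval is an assumption. The base case of 14 days matches a day-14 surge in a 28-day cycle.

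| Assumed interval (days) | Expected surge days for 26- to 32-day cycles | Lengths with expected surge after day 16 |
|---|---|---|
| 12 | 14-20 | 29, 30, 31, 32 |
| 13 | 13-19 | 30, 31, 32 |
| 14 | 12-18 | 31, 32 |
| 15 | 11-17 | 32 |
| 16 | 10-16 | none |

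**4. Allow for variation.** Assume a 14-day mean interval and standard deviations of 1 day for a woman's own cycle length and 1 day for the interval. The surge-day SD is then √(1² + 1²) = 1.41. For length L, the monthly miss probability, counting both ends of the window, is

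p = 1 − Φ[(16.5 − (L − 14))/1.41] + Φ[(9.5 − (L − 14))/1.41].

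| L | Expected day | p | p² (two in a row) | Weight if centred on 28 |
|---|---|---|---|---|
| 26 | 12 | 0.039 | 0.002 | 0.117 |
| 27 | 13 | 0.013 | 0.000 | 0.222 |
| 28 | 14 | 0.039 | 0.002 | 0.275 |
| 29 | 15 | 0.144 | 0.021 | 0.222 |
| 30 | 16 | 0.362 | 0.131 | 0.117 |
| 31 | 17 | 0.638 | 0.407 | 0.040 |
| 32 | 18 | 0.856 | 0.733 | 0.009 |

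The last column is a normal distribution with mean 28 and SD 1.5, rounded to whole days and truncated to 26-32. Months are taken as independent given a woman's usual length.

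- Lengths uniform over 26-32: the p column sums to 2.091, and 2.091/7 = 0.299. The p² column sums to about 1.29, and 1.29/7 ≈ 0.18. Simulation gives 29.8% and 18.4%.
- Lengths centred on 28: the weighted means are 0.125 and 0.043.
- Lengths centred on 29: about 23% and 11% by simulation.
- Uniform lengths with a mean interval of 13 or 15 days: monthly misses of 43% or 20%.

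**5. Before or after randomisation.** Month 2 uses the same window and precedes randomisation in Month 3, so it already removes some of the women at risk. Among women caught at the first attempt in Month 2, with one repeat month allowed in each of Months 3 and 5, the later loss is

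Σw(1 − p)[1 − (1 − p²)²] / Σw(1 − p),

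which is about 12% for uniform lengths and about 4% for lengths centred on 28.

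**The case against.** The contradiction within the documents is a single day, 16 against 17, and could be a counting slip in section 6.2.2. Everything beyond that rests on a surge-to-menses interval and a spread of cycle lengths that the plan does not give. At a fixed 16-day interval no eligible length has its expected surge outside the window. The result also moves more than fourfold (4% to 18% for two misses) with the assumed spread alone. This stands, and it is why the percentages are conditional and the wording is that women can be, not will be, misclassified.

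The consequences are also milder than they may first appear. Section 3 postpones after one miss, so the Month 2 baseline is delayed rather than lost, and section 5.1 allows a repeat month. Some of the loss falls before randomisation.

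A reader might infer that women with 31- or 32-day cycles are missed every month. Even in the base case, 1 − 0.638 = 36% and 1 − 0.856 = 14% of their tested months are caught. A reader might also infer that the comparison of the two treatments is biased. The documents do not support that: the window is the same in both periods, nothing links a missed surge to treatment order, and each woman serves as her own control.

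What the objection does not remove is that no section extends testing, ties the start day to a woman's cycle length, or gives a second way to confirm ovulation before the postponement and discontinuation rules apply.

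**Conclusion.** The point holds at moderate severity. That testing stops on day 16 while ovulation is accepted to day 17 follows from the text without any outside figure. The mismatch with 26- to 32-day eligibility depends on the interval: at 14 days it affects 31- and 32-day cycles, at 13 days 30 to 32, at 15 days only 32, and at 16 days none. With a 14-day interval and 1-day SDs, about 12% to 30% of tested months are missed, and about 4% to 18% of women miss two in a row. Those figures cover unselected women and so combine loss before and after randomisation. The number of women actually affected cannot be computed from the documents. The harm is to feasibility and generalisability: delay, avoidable dropout and under-representation of longer cycles.

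**What to change.** - Reconcile the testing window in sections 6.2, 6.2.2, 6.2.4 and 15 with the ovulation range in section 6.2.2 and the eligible cycle lengths in sections 4.1 and 9.3. The LH measurement window should cover the days the plan itself accepts and those expected across eligible lengths. Using each woman's recorded cycle length, or continuing to test past day 16 when no surge has been seen, are two examples.
- Align the hand-out of kits and equipment (sections 5.1, 6.2.2, 10.3.3 and 15) with whatever window is chosen. A rigid formula needs care. Starting at cycle length minus 17, for instance, gives day 9 for a 26-day cycle, although the hand-out visit may be as late as day 10. It gives day 15 for a 32-day cycle, leaving accepted days 10-14 untested.
- In sections 3, 4.2 and 5.1, record no surge detected within the window separately from failure to ovulate, and do not count the first as the second when the window did not cover the expected surge day. The postponement and discontinuation rules themselves remain for the sponsor to settle.
- Report undetected surges by cycle length, separately before and after randomisation.

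The cost is protocol wording plus a few more test strips or an individual start date per woman. Treatment timing relative to the surge does not change.

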6.2.3 Blinding

The principal investigator and clinical rater will remain blind to treatment condition until completion or discontinuation of participant from study. As patients will be coded, one statistician and technician and supervisor running assays also will be blind to patient name and treatment condition. Members of the Data Safety Monitoring Committee will review records in which patient names are coded, unless the code needs to be broken in the event of an adverse outcome. All other lab personnel will not be blind to treatment as the study coordinator and research associate prepare patient equipment and instruct patients on proper completion of the treatment protocol, the data manager and quality assurance officer enter all data into the database (including treatment condition). Due to the nature of the treatment (sleep, light intervention), patients will not be blind to condition.

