7.1 Specification of Safety Parameters

Risks to patients in this protocol are low and are detailed as follows:

Affect and Anxiety:

Premenstrual symptoms may become worse leading to depression, anxiety, irritability and rarely suicidality. It is anticipated that these studies will not be greatly different from spending nights at home with some added measurements and interventions. The added measures may add some disruption and anxiety to daily schedules.

Urine Collection, Sleep/Activity:

The risks of urine collection are minimal and may include inconvenience with collection of samples and completion of forms. Sleep and activity measures are non-invasive, but may cause some skin irritation and/or discomfort on the wrist where the Actiwatch is worn.

Effects of Bright Light Treatment:

Since most of us are exposed to fluorescent light in our everyday lives, we do not anticipate that exposure to bright light per se will pose any special physical, psychological, social or legal risks. The intensity planned is less intense than bright sunlight, which normally exceeds 10,000-50,000 lux. Although 1,350 lux is more intense than common indoor room lighting during a 16-hour day, the average patient would receive more radiation from room lighting than from 1-2 hours of special lighting. Thus, the treatment is expected to be less hazardous than going for a walk or going to the beach. No special side effects apart from mild sleepiness (the patient needs to be awake for the light exposure and evening light may potentially disrupt sleep onset) are anticipated. It should be noted that sleep deprivation has been reported to benefit depressed patients. The possibility that the bright light treatment might potentiate a depressed patient's risk of switching into mania is recognized, although we have not seen this effect in previous studies of PMDD patients and we will exclude bipolar patients with mania from the study. If hypomania occurs, the light would be discontinued and appropriate referral and treatment with psychotropic medication, if needed, would be given.

Effects of Wake Therapy or Partial Sleep Deprivation:

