The potential risks include fatigue. Subjects will be encouraged to stay at home the day after wake therapy or, if driving, arrange alternative transportation. In previous studies of one night of total wake therapy in PMDD patients, subjects felt energized and wished to return to work or other daily activities. Previous studies also included two consecutive nights of partial wake therapy. We anticipate fewer problems in this study with only one night of partial wake therapy.

The following risk-management procedures will be used:

Depression, Anxiety, Suicidality, Mania:

To guard against adverse effects, all subjects will have a complete psychiatric history administered by a certified clinician. By monitoring mood twice daily and by providing weekly ratings by trained clinicians, we expect to detect any problems with mood before they become severe. Known bipolar patients are excluded to reduce the risk of mania occurring. Suicidal ideation will be monitored by the Clinical Rater at the time of HRSD administration. Patients are instructed to call the Rater, Study Coordinator, Research Associate or on-call psychiatrist if these symptoms occur. Suicidal ideation will be evaluated by both the Clinical rater and PI to determine the best course of action. A licensed psychiatrist will always be on-call to subjects should any psychiatric emergency arise. If needed, patients will be referred for appropriate treatment including inpatient hospitalization if warranted.

Urine Collections:

Trained staff will instruct participants in the proper method of urine collections.

Wake Therapy:

To ensure sufficient wakefulness after the wake therapy interventions, the patient is encouraged to stay at home, not drive or operate machinery and arrange for alternate transportation, for which they will be reimbursed. To avoid the induction of mania, bipolar patients are excluded.

Actiwatch:

Equipment will be checked regularly and its use by subjects overseen by specifically trained personnel to ensure maximum safety and comfort.

Pregnancy:

Subjects are warned not to rely on "time of the month" for contraception.

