10. DATA COLLECTION AND QUALITY ASSURANCE

10.1 Data Collection Forms

Data will be collected according to the schedule outlined in section 6.1. The blind clinical rater will collect all mood forms (Hamilton, BDI, BAI, PGWI, DMRs, SCID, etc.). All other forms (screening, consents, actigraphy, urine collection, side effects, urine toxicology, ovulation, etc.) will be collected by the study coordinator and/or research associate, who are not blind to the study condition. Forms will not contain any patient identifiers; only patient numbers corresponding to each participant in accordance to the confidentiality protocols stipulated in section 11.3 below.

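### Section 6.2 sends the Month 3 side-effects and sleep forms to the blinded HRSD rater, and they could reveal the Month 5 arm

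*Combined protocol and SAP*

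**What the plan says.** **Who is blind.** Section 6.2.3 states that "Due to the nature of the treatment (sleep, light intervention), patients will not be blind to condition". Of the assessors it says: "The principal investigator and clinical rater will remain blind to treatment condition until completion or discontinuation of participant from study". The study coordinator and research associate are not blind (sections 5.2 and 6.2.3).

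**Who scores the HRSD.** Section 6.2: "Objective ratings (HRSD and SCID) will be administered, collected, scored and reviewed by the Clinical Rater immediately upon completion by the patient". The HRSD and SIGH-SAD atypical items belong to the primary mood outcome (section 9.5.1).

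**Where the self-rated forms go.** Section 6.2 lists the subjective ratings, including the PSQI and ending with "Sleep Quality Ratings, Side Effects Checklists, Global Assessment of Treatment Effectiveness". It says that they "will be collected and scored by the Research Associate for review by the Clinical Rater upon completion by the patient".

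**When they are due.** Section 6.2.4 puts the PSQI and the sleep-quality scale at LHS+8-9 in Months 3 and 5. Section 9.5.2 puts the Side Effects Checklist one to two days after each intervention. Appendix I has forms returned to the laboratory at LHS+11.

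**What they may show.** Sections 5.1 and 7.1 say that "evening light may potentially disrupt sleep onset". Evening light is given only with EWT.

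**The concern.** Section 6.2 and section 6.2.3 ask the same person for two things that do not sit well together. The rater must not know the arm, yet is to review, with no delay or masking, the forms on which a treatment-specific effect on sleep would be recorded.

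At stake is the interview-based part of the primary mood outcome. Hypothesis 1.A is directional: LWT+AM BWL is expected to lower scores more than EWT+PM BWL. A rater who has worked out the arm could, without intending to, score in that direction. The crossover makes this worse, because each woman receives the opposite treatment in Month 5. No section tells participants not to disclose their treatment to the rater, or checks whether the rater stayed blind.

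**Working it through.** There is no plan figure to reproduce. The check sets the sections side by side, counts the exposed ratings, and then illustrates what a given bias would do.

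**1. Which forms can matter.**

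| Form | Due | To rater under 6.2 | Before Month 5 ratings |
|---|---|---|---|
| PSQI | LHS+8-9, Months 3 and 5 (6.2.4) | yes | yes |
| Sleep-quality scale | LHS+8-9, Months 3 and 5 (6.2.4) | yes | yes |
| Side Effects Checklist | 1-2 days after each intervention (9.5.2) | yes | yes, on the timing in 9.5.2 |
| Global Assessment | after both treatments, at the final visit (9.5.2, 6.2.6) | yes | no |

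The Global Assessment therefore drops out.

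**2. Latest plausible timing.** Suppose the rater sees the Month 3 forms only when they come back at LHS+11. Cycles are 26-32 days (section 4.1) and treatments are two cycles apart. The shortest gap is 2 × 26 = 52 days, so the forms are in hand about 52 − 11 = 41 days before the first Month 5 rating. The Month 3 post-treatment HRSD, by contrast, is taken at LHS+8-9 (section 6.2.4; Figure 1 has LHS+7/8), before LHS+11. It would be exposed only by same-day review, which the wording of 6.2 permits but nothing shows to be intended.

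**3. What a guess reveals.** With two treatments and two periods, arm in Month 5 = the other of (arm in Month 3). The evening-light cue can be present in Month 3 only for women who had PM light first, which under 1:1 randomisation is about 40 × 1/2 = 20 of 40. In Month 5 those women receive LWT+AM BWL, the favoured arm. For the other half, absence of the complaint is weaker evidence.

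**4. Ratings exposed.** Hamilton ratings from Month 3 on (sections 6.2.4 to 6.2.6): Month 3, four (LHS, +1, +2, +8-9); Month 4, one; Month 5, four; final visit, one; follow-up, one. Total 4 + 1 + 4 + 1 + 1 = 11. After the Month 3 forms: 1 + 4 + 1 + 1 = 7. The primary contrast in section 9.5.1 is baseline (Month 2) to post-intervention (Months 3 and 5), so only the four Month 5 ratings lie in an intervention month of that contrast.

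**5. Illustration of size.** Let p be the share of women whose Month 5 arm the rater infers correctly, and δ the resulting shift in HRSD points toward the hypothesis. In either sequence the shift moves the within-woman difference the same way, so the mean bias is b = p × δ. Neither p nor δ is in the documents. Take N = 40 and treat the ±9 in section 9.2 as the SD of the within-woman difference (an assumption). Under a simple paired t-test with no true difference, the two-sided rejection probability is P(|T| > t at 0.975 with 39 df), with T noncentral t and noncentrality b × √40 / 9:

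| b (HRSD points) | Rejection probability |
|---|---|
| 0 | 5.0% |
| 0.5 | 6.4% |
| 1 | 10.5% |
| 1.5 | 17.7% |
| 2 | 27.8% |

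A mean bias of 1 point needs, for example, p = 0.25 (10 of 40) with δ = 4, or p = 0.50 (20 of 40) with δ = 2.

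**The case against.** The strongest reply is that the cue is weak. The sleep-onset remark is a possibility in parentheses, insomnia or hypersomnia is itself one of the PMDD symptoms in section 4.3, and both arms include a night of partial sleep loss. A poor PSQI therefore says little about the arm, and the checklist items are not shown. This stands as a limit on size. It does not make the routing useful to the blind.

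Checklist timing is also less than certain. Section 6.2.4 does not list the checklist among treatment-visit measures, and Appendix I has side effects reviewed at the final visit. Section 9.5.2 nevertheless places it in Months 3 and 5, and the two sleep forms are due in Month 3 in any case.

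The rater also interviews unblinded patients by telephone, which may be the larger leak. That is a reason to brief participants, not to keep an avoidable second route. And section 7.3 uses the checklists to assess safety, so someone must read them; the documents do not say that it must be the HRSD scorer.

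Four stronger readings are tempting but not supported:

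- A reader might infer that section 10.1 contradicts 6.2 on side-effects forms. It does not. Both have unblinded staff collect them, and 10.1 is silent on review. The two sections do differ on who collects the BDI, BAI, PGWI and DMR, which is a separate matter.
- A reader might infer unblinding in both periods. Step 2 shows that this is not established for Month 3.
- A reader might count all seven later ratings against the primary outcome. Three of them, at washout, final visit and follow-up, are outside its contrast.
- A reader might treat the symptom calls in section 7.1 as a side-effects route: "Patients are instructed to call the Rater, Study Coordinator, Research Associate or on-call psychiatrist if these symptoms occur". The symptoms meant there are mood problems and suicidal ideation, which are not specific to an arm.

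**Conclusion.** The point holds in a limited form. Followed as written, section 6.2 gives the blinded rater three Month 3 forms that may carry a cue to the arm, before any Month 5 rating is made. The four Month 5 interview-based ratings (HRSD, atypical, SIGH-SAD) are at risk. Self-rated scales are outside this point, since patients know their arm anyway, and 6-SMT is assayed blind.

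The conclusion rests on the checklist timing in section 9.5.2, on the rater acting on 6.2 no later than shortly after form return, and on the cue being right for at least some women. The share unblinded and the size of any bias are unknown. The table in the working shows only that a mean bias of 1 HRSD point would roughly double the nominal 5% error. This is an inexpensive improvement to the plan, not evidence that the mood results would be invalid.

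**What to change.** - In section 6.2, withhold the Side Effects Checklist, PSQI and Sleep Quality Ratings from the Clinical Rater until the woman has completed all her ratings, including follow-up.
- Assign routine review of these three forms to the study coordinator or research associate, who are already unblinded.
- Add an instruction that participants should not describe their treatment or its timing to the rater.
- Leave the symptom-call and suicidality pathway in section 7.1 as it is. Note only that sections 6.2, 6.2.3 and 7.1 must be reconciled on the rater's role.

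The cost is a change of wording with existing staff. The downside is that the rater loses routine sight of these forms, so the coordinator must escalate any concern through the safety channels already in place.
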